### **CON Clinics:**

Providers will get a list of eligible patients DM-ADRD initially, giving them the opportunity to follow the decisional guidance. In addition, the guideline will specify cognitive screening in DM patients,  $\geq 75$  years with high or low HbA1cs or BP's because we suspect that these values may represent self-management red flags due to cognitive (especially memory and executive) impairment. During training the CON providers will be encouraged to do cognitive screening as well as follow the guidelines in general. Clinics can decide who does the cognitive screen, such as a RN or MA, using the MiniCog™ we will address this issue in the guideline and during provider training. Per guidelines, any patient with a MiniCogTM score  $< 3$  of 5 should have further cognitive assessment per the guideline and preferences of the patient/caregiver dyad. These patients will also become eligible for the evaluation and can be identified by periodic research staff EHR identification of patients with DM-ADRD diagnoses in the CON clinics. When identified we will enroll them for the evaluation (4.2). As with INT clinic patients, we anticipate patient/caregiver loss over the 3 years of the study and the sample will be refreshed with patients with new diagnoses and who are new to the clinic. The investigators will visit CON clinics yearly to discuss care of patients with DM-ADRD. These meetings will serve to answer questions, get feedback from PCPs and provide general feedback on the progress of the quality improvement program.

## **5. Methods and Procedures (Evaluation)**

### **5.1 Screening and Identification**

We will use NYU Langone Health Epic to identify patients in the INT and CON clinics who meet inclusion and exclusion criteria listed in Section 3.2.

There will be three levels of screening:

- **Level 1:** Initial screening will be automated by settings in the EHR that generate a report based on inclusion criteria (above).
- **Level 2:** The initial list of patients generated by the EHR will be screened by the RA first through chart review for eligibility based on exclusion criteria (see Section 3.2). Should the patient not meet inclusion criteria, for example they don't actually have a diagnosis of diabetes, or speak English or Spanish; the patient will be removed from the list of potentially eligible patients.
- **Level 3:** Those patients who remain eligible following chart review to their PCP's in the INT clinics to notify them about their patients with DM-ADRD. The PCP's will be encouraged to review their list and decide if a patient is misclassified or inappropriate; some will review the lists and some will not. Any patient a PCP indicates as inappropriate or misclassified will be ineligible and will be screen failures. The amended list of eligible patients with both DM and ADRD for both the INT and CON clinics will go back to the RM who will send a letter to the patients informing the patients/caregiver of the quality improvement program and of a potential telephonic survey.

While eligible patients are easily identified by Epic, their caregivers (the respondents to the surveys and interviews to evaluate the quality improvement program) are not always listed in the patient chart. To identify an appropriate caregiver, a letter from the primary care physician will ask the patient to read the letter and then give it to their caregiver. The letter will explain the quality program briefly and state that a research assistant will call the patient's home unless they do not want to be called.

If the dyad, for whatever reason, does not want to participate in a call, they will be asked to opt out using the Standard Operating Procedure (SOP) of NYU Langone Health as outlined in SOP #HSR-312, Version Number 2.0. This SOP states that patients are able to opt-out of the Direct Recruitment process either by [contact]) or email ([contact]). Patients who wish to opt out must provide at least three of the following identifiers:

1. Full name
2. Date of birth
3. Address
4. Medical record number

The opt-out phone line and email account are managed by Office of Science and Research (OSR) personnel. Authorized OSR personnel and the Senior Director of Compliance and Privacy are the only individuals authorized to add patients to the opt out list. Should we receive a patient opt out request we will instruct the patient to follow this process. OSR will process this request upon receipt of all required information, and update the patient status in a tracking sheet and in Epic to "Do Not Contact."

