### 1.2 Specific Aims

Specific Aims of the R33 Enhanced Quality In Primary Care for Elders with Diabetes-ADRD (EQUIPED-ADRD) are:

- 1) Implement and evaluate a pragmatic trial in a large healthcare system using cluster randomization, and the practice change framework, that will: manage people with co-occurring DM and ADRD according to the guidelines developed to test our hypotheses and identify additional patients with cognitive impairment and inappropriate DM management.
- 2) Test whether EQUIPED-ADRD will increase the proportion of intervention patients who are in desirable glycemic and blood pressure ranges compared to control patients.
- 3) Test whether the EQUIPED-ADRD intervention will improve dyad perception of care quality and reduce treatment burden.
- 4) Test whether dementia symptoms will deteriorate less in intervention subjects compared to controls.

**Exploratory Aim.** Test whether intervention subjects will use fewer health care services than controls and will have less cognitive decline associated with desired changes in glycemic and blood pressure control.

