### **INT Clinics:**

In the INT clinics we will introduce the panel manager (PM) to all clinic staff and develop processes for interaction. The PM will work with INT clinic providers to individualize communication methods between the PCP and PM. Each month INT clinic providers will get a list of eligible patients who have appointments with them in the coming month - those with diagnoses of DM-ADRD and those 75 and older with DM who are out of range for HbA1c or BP. This process gives providers monthly reminders about the ongoing quality improvement study and is a more intensive form of QI intervention than provided to CON clinics.

Because this is a pragmatic trial, the clinical team and a project-funded PM will deliver the intervention, fitting it as closely as possible into usual clinical workflow. The clinical team includes PCPs, occasional APNs and PAs (who function as PCPs), RN's, MA's, office staff, and clinic onsite administration. The PM will be part of the team; PMs providing chronic disease self-management support (usually telephonic) are clinic team members in many healthcare systems.

We will assign two PMs to 9 randomly selected INT clinics. Each PM will have 4.5 INT clinics and will engage and focus on their first clinics in a randomly ordered step-wise fashion working within 1-2 clinics over a focused 3-month period before moving on to the next 1-2 clinics for 3 months, then the last 1-2 clinics for 3 months. Our preliminary data suggests 20-50 patients per INT clinic with DM-ADRD  $\geq 65$  years; and about an equal number with DM without ADRD who will screen positive for cognitive impairment, most of whom are  $\geq 75$  years and identified by HbA1c/BP over or under treatment, or identified by provider referral, which we will allow. With 9 INT clinics, given our preliminary data about patient numbers, each PM will have an anticipated 300 dyads. PMs can engage about 33 patients/month, making initial 300 patient/CG contact in 9 months.

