We will train intervention PMs in DM and ADRD management for INT clinics. Training will include one-on-one sessions with the mPI's and co-I's, suggested reading, shadowing relevant clinicians, such as social workers in the Alzheimer's Disease Center and geriatrics clinic, and other relevant activities. We expect training will require one month's duration with subsequent continuous learning activities that include continuing meetings with mPIs and co-I's and travel to national conferences.

**PM Activities.** The PM will reach out to eligible patients with diagnosed DM-ADRD (see section 4.3) and  $\geq 75$  year-old patients with over- and under-treatment of HbA1c/BP for cognitive screening using IQ-CODE as defined in the Guideline. For those with a positive screen, in coordination with the PCP, the PM will facilitate further cognitive evaluation. These patients will become part of the quality improvement intervention. The PM will begin telephonic assessment and DM management education of DM-ADRD patients around the time of the scheduled visit (either just before or just after). The PM will conduct a detailed psychosocial and needs assessment with each willing CG and assess the patient based on both a standardized assessment and clinical judgement. The PM will also engage those CGs who live far from the patient and who manage the patient remotely through paid home health aids (HHA). The CG psychosocial assessment will focus on diabetic management support and family dementia CG support providing referrals as needed to well established New York City programs. The PM will provide PCPs with evaluation data, DM-relevant care suggestions and facilitate PCP visits for care reassessment as clinically appropriate. The PM will assist the PCP and the dyad with developing individualized DM management targets and re-evaluating these targets over time. The PM will maintain dyad follow-ups and monitor patient-level data using EHR follow-up data as per usual clinical care, and an Epic-generated report for relevant issues. The PM will also address dyad goals and treatment preferences and assist with communicating these with the PCP. A key part of PM activity will be determining with each PCP their preferred method of communication (e.g., Epic messaging, order pending, periodic phone calls, etc).

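### Section 5.1 writes a PCP removal step for INT clinics only, on an open-ended ground and after clinic randomisation; unless reconciled with the rest of the protocol, it risks selection bias in the HbA1c comparison

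*Combined protocol and SAP*

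**What the plan says.** Section 1.2 sets the trial "in a large healthcare system using cluster randomization", so a clinic's arm is fixed before its patients are screened. Section 5.1 then describes three levels of screening. Level 1 (the automated EHR report) and Level 2 (chart review by the research assistant) make no distinction by arm. Level 3 does: "Those patients who remain eligible following chart review to their PCP's in the INT clinics to notify them about their patients with DM-ADRD". The sentence has lost its verb, but the only recipients it names are INT PCPs. PCPs are then asked to review their list. On uptake the protocol says "some will review the lists and some will not", and on consequence: "Any patient a PCP indicates as inappropriate or misclassified will be ineligible and will be screen failures". The next sentence reads "The amended list of eligible patients with both DM and ADRD for both the INT and CON clinics will go back to the RM".

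Section 4 describes two other lists. For CON clinics: "Providers will get a list of eligible patients DM-ADRD initially, giving them the opportunity to follow the decisional guidance". For INT clinics: "Each month INT clinic providers will get a list of eligible patients who have appointments with them in the coming month". Section 4 presents the monthly INT lists as reminders.

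The exclusion criteria (the second section numbered 3.2) cover clinic, age, diabetes, cognitive status, end-stage or terminal illness, lack of a caregiver, and hearing. A PCP's view that a patient is inappropriate is not among them.

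**The concern.** Randomising clinics makes the clinics comparable. It does not protect the patient samples if patients are then selected differently by arm. INT PCPs know their allocation, because they work with the panel manager. If they alone can strike patients, and on a ground wider than the written criteria, the INT sample is what remains after a filter that the CON sample never meets.

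The primary outcome is HbA1c on target. Section 4 also gives INT providers reports on the proportion of their patients in range. Removal related to glycaemic control is therefore plausible, although nothing in the documents shows that it would happen. Uneven use of the review would add variation between INT clinics.

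Section 7 does not address this. It relies on randomisation, considers adjustment for observed imbalances, and directs its sensitivity analyses at missing outcomes. Patients struck at Level 3 never enrol, so they are not missing outcomes in that sense.

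**Working it through.** **Is the removal step arm-specific?**

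- *Recipients at Level 3:* INT PCPs are the only ones named.
- *Who may remove:* Section 5.1 says a PCP, without naming an arm. The nearest PCPs in the text are those in INT clinics.
- *Amended list:* it covers both arms. This fits review in both arms. It also fits a combined list of which only the INT part was changed.
- *CON list in Section 4:* it is given once, for use with the guidance, and no review or removal is described. For CON patients identified later through the EHR, Section 4 goes from identification to enrolment with no PCP step between.
- *Invitation letter:* Section 5.2.1 lists it for INT only, while Section 5.1 implies both arms. Recruitment steps are thus written unevenly elsewhere too.

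INT-only removal is the more natural reading, but it is not certain.

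**How large could the effect be?** The documents give no on-target rate, ICC, effect size, power or expected removal rate, so there is no planned figure to reproduce. What follows is an illustration with no true intervention effect and removal in INT only.

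From the documents: 500 patients per arm (Section 1.1), 9 clinics per arm (Section 3.1, which also speaks of 20 practices), two-sided alpha 0.05 (Section 7). Assumed: on-target rate p = 0.50; r, the share removed among INT patients who would otherwise have enrolled; g, the amount by which their on-target rate falls below p; and the ICC.

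Rate among those kept = (p − r(p − g)) / (1 − r), so the spurious INT minus CON difference is r·g / (1 − r).

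- r = 0.05, g = 0.10: 0.005 / 0.95 = 0.5 points
- r = 0.10, g = 0.20: 0.020 / 0.90 = 2.2 points
- r = 0.20, g = 0.30: 0.060 / 0.80 = 7.5 points

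If the gap is measured between kept and removed patients instead, the difference is r × gap, giving 0.5, 2.0 and 6.0 points.

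For the false-positive rate: m = 500 / 9 = 55.6 patients per clinic and design effect 1 + (m − 1) × ICC, which is 1.55 at ICC 0.01 and 3.73 at ICC 0.05. The effective number per arm is 500 divided by the design effect. A two-sided normal approximation gives:

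| r | g | Spurious difference | Odds ratio | ICC 0 | ICC 0.01 | ICC 0.05 |
|---|---|---|---|---|---|---|
| any | 0 | 0 | 1.00 | 5.0% | 5.0% | 5.0% |
| 5% | 10 points | 0.5 points | 1.02 | 5.3% | 5.2% | 5.1% |
| 10% | 20 points | 2.2 points | 1.09 | 10.8% | 8.7% | 6.5% |
| 20% | 30 points | 7.5 points | 1.35 | 66.5% | 48.4% | 23.5% |

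With about 18 clusters, a t reference would lower these rates slightly. If PCPs tended to strike well-controlled patients, the sign would reverse. The same removal rule in both arms gives an expected difference of zero in this model.

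**The case against.** The strongest reply is that the protocol may intend PCP review in both arms. The Level 3 sentence is visibly damaged, the removal sentence names no arm, the amended list covers both arms, and CON providers do receive a list. This stands as a reason for caution. It does not remove the need to act: if both arms were meant, Level 3 still names only INT, and staff would follow it as written.

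Three stronger readings are tempting, and the documents do not support them.

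- *That only INT PCPs see a list of eligible patients.* Section 4 gives CON providers one at the start. Only the removal step appears to be confined to INT.
- *That the monthly INT lists renew the power to remove.* Section 4 treats them as reminders and attaches no removal right. If a list given for another purpose confers no removal step on CON, the same must hold for INT.
- *That bias is certain, with CON keeping miscoded or near-terminal patients whom INT drops.* Dementia status and terminal illness are written exclusions, and Level 2 chart review applies to both arms. It should catch many such patients before any PCP is asked.

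Adjustment is also not worthless. Baseline HbA1c status is collected, and adjusting for it could offset part of any selection on glycaemia. It cannot bring back the struck patients or balance what was not measured.

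**Conclusion.** The point holds as a contradiction to be reconciled and as a risk of selection bias. The only PCP removal step written out names INT clinics, operates after randomisation by clinicians who know their arm, and allows a ground outside the exclusion criteria. No CON counterpart is described, and no analysis compensates.

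How much it matters depends on two unknowns: how many would-be participants are struck, and whether striking is related to HbA1c control. Under the assumed ranges the spurious difference runs from nil to 7.5 points. The middle case (2.2 points) raises the false-positive rate modestly; the extreme case raises it seriously. These figures show scale only and predict nothing. The matter should still be settled, because the selection cannot be examined afterwards unless the pre-review list is kept.

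**What to change.** 1. **Make Level 3 the same in both arms.** Either give INT and CON PCPs one review of the Level 2 list before enrolment, or drop the PCP removal step and rely on chart review by the research assistant. The first option can build on the initial list that CON providers already receive. The monthly INT lists should not be extended to CON, since they are part of the intervention contrast.
2. **Limit removals** to the written exclusion criteria, with a coded reason for each.
3. **Reconcile the text:** restore the missing verb in Level 3, state who may amend the list, and bring the CON paragraph of Section 4 into line.
4. **Report** numbers removed and reasons, by clinic and arm.
5. **Keep the pre-review Level 2 list** and, as far as IRB and consent terms allow, repeat the HbA1c on-target comparison in everyone on it. Section 5.4 (item 4) already plans a de-identified Epic extract for patients in intervention and control clinics. Whether it may be used for patients who were struck and never consented is not stated and must be confirmed.

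The cost is revised wording, at most a single review request to CON PCPs, and one sensitivity analysis. Shared review means slightly more contact between CON PCPs and the list. Dropping the review means that some letters may go to patients whom their PCP considers misclassified.

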## 5.2 Consent Procedures and Documentation

### 5.2.1 Process of Consent

The patient and caregiver (dyad) is enrolled in the study (the evaluation of the RCT of a quality

improvement program) when verbal consent (or assent, see E3) is obtained from the patient and caregiver.

### ***Verbal Consent***

We are requesting a HIPPA waiver of authorization and documentation of consent in order for caregivers and patients to give verbal consent for the survey, qualitative interview and use of patient data (EHR and claims).

We request the use of verbal consent and a waiver for documentation of consent because:

- 1) This study presents no more than minimal risks to privacy for subjects. All survey data obtained will be stored in HIPPA compliant REDCap library accessible only to the IRB approved study team. All data exported from REDCap will be fully de-identified, and contain no subject identifiers.
- 2) It would not be possible to conduct this study without the use and analysis of subject PHI to evaluate the improvement in care for patients, and burden for caregivers. Investigators will take all precautions, outlined in Section 6.2 Protection Against Risks, to protect the privacy and maintain confidentiality of subjects.
- 3) Surveys and qualitative interviews will occur by telephone making written consent infeasible given enrollment of 1,000 patients and caregiver dyads.
- 4) Verbal consent provides opportunity to fully explain study procedures, risks and benefits and assess for capacity to consent, an important and necessary procedure in this population both for patients and caregivers.
- 5) Requiring an elderly person to recall, interpret, and understand requested instructions for consent purposes through mail will result in many unreturned documents and an unfair prevention of participation for those persons who want to participate but are otherwise “unable” to.
- 6) Finally, in the clinical space, where HIPPA rules are equally enforced, we conduct verbal consents for release of information when written consents are not feasible and complete that authorization by documentation from a legally authorized representative (in this case, a physician).

### ***Step by step process of consent:***

1. **INT:** RA mails letter (see Patient Letter) to patients in INT clinic signed by the clinic director, lead physician, or primary provider (depending on clinic preference) informing them about EQUIPED quality improvement program and evaluation.
2. **INT and CON:** RA calls eligible patient and/or caregiver using contact information from patient chart in EHR. If caregiver information is not available in the chart, the RA will ask the patient for caregiver contact information.
3. **INT and CON:** RA screen Patient and/or Caregiver for Capacity to Consent (See section E3)
  - a. If the patient demonstrates capacity, the patient is deemed able to provide verbal consent to have the study team talk to the caregiver to obtain their verbal consent

and to have the study personal obtain and analyze health data (medical records and claims).

- b. If the patient does not have capacity and assents to the study, the RA is able to speak to the caregiver who provides verbal consent for the caregiver survey , and the Health Care Proxy (HCP) (who may or may not be the caregiver) provides verbal consent for study personnel to obtain and analyze the patients' health data (medical records and claims).
- c. If the patient does not have capacity, and refuses (no assent), the dyad will not be enrolled although the clinical team (Panel Manager) can re-contact that dyad over time to offer improved care quality.

4. **INT and CON:** If the caregiver demonstrates capacity (screened using Capacity to Consent, at the discretion of the RA) verbal consent will be documented by the RA in REDCap and the caregiver will be consented to participate in the study. Caregiver consent covers participation in 4 telephone surveys.

A healthcare proxy is an individual who is designated as a representative/agent through a health care proxy signed by both the subject and the appointed representative/agent. For a health care proxy to be effective, it must have been signed at a time when the subject had decision-making capacity. In addition, the health care proxy must not specifically prohibit research. Determination of the legal authority of a surrogate will be obtained through Epic, or verbally by the patient and/or caregiver.

Potential subjects will be told that their involvement in the study is completely voluntary and that they can withdraw from the study at any point. Caregivers may themselves be elderly and might have cognitive impairment such that it impacts their capacity to consent to research. For all potential participants, we will assess the individual's ability to provide informed consent using IRB approved interview procedures to assess capacity to consent for research. Some subjects may be too hearing impaired to communicate by telephone and the telephone interview is designed to assess for this potential problem and mitigate this issue when possible but this might impair one's capacity to consent. Although we have conducted numerous studies with elderly subjects, this has been a rare occurrence. Nonetheless we will not enroll any caregiver participant who cannot communicate by telephone.

If the patient demonstrates capacity (See E3. Subject Capacity), the patient is deemed able to provide verbal consent to have the RA talk to the caregiver and to have the study personal obtain and analyze health data. If the patient does not have capacity and assents the caregiver will provide verbal consent for the caregiver survey, and the HCP (who may or may not be the caregiver) provides verbal consent for the health data (medical records and claims). If the patient refuses (with or without capacity), the dyad will not be enrolled although the clinical team can re-contact that dyad over time to offer improved quality care.

If the caregiver, after following our standard consent procedures, demonstrates capacity using the below questions, verbal consent will be documented and the caregiver will be consented to the study. Caregiver consent covers participation in 4 telephone surveys. Patient (with capacity) or HCP (if patient assents but does not have capacity) will provide verbal consent for health data (EHR and claims information). The research assistant will document this agreement to participate using a standardized form kept for documentation purposes.

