### 3.2 Inclusion Criteria

Patient:

- 1) Patient must receive care at one of the INT or CON clinics.
- 2) Patient must be 65 years and older.
- 3) Patient must have DM diagnosis.
- 4) Patient must have documented cognitive impairment **or** an ADRD diagnosis (ICD-10 diagnosis in Epic).
- 5) Patient must have someone who is identified as a family or friend who provides caregiving assistance.

Caregiver:

- 1) Caregiver must have adequate knowledge of identified patient and/or participate in that member's healthcare decisions.
- 2) Caregiver must be English or Spanish speaking.
- 3) Caregiver must demonstrate capacity to consent to research participation.
- 4) Caregiver must be at least 21 years old.

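### Sections 5.1 and 5.2.1 disagree on whether control patients receive the advance letter; if 5.2.1 is followed, the arms are recruited differently after clinic randomisation

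*Combined protocol and SAP*

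**What the plan says.** **Step list under Section 5.2.1.** Step 1 carries the label INT and reads "RA mails letter (see Patient Letter) to patients in INT clinic signed by the clinic director"; a lead physician or the primary provider may sign instead. Steps 2 to 4 (the call, the capacity screen, caregiver consent) each carry the label INT and CON. In step 2, where the chart names no caregiver, the research assistant (RA) asks the patient for the details by telephone.

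**Section 5.1.** At the third screening level, the amended list "for both the INT and CON clinics will go back to the RM who will send a letter to the patients", telling them about the program and a possible telephone survey. The section then notes that caregivers "are not always listed in the patient chart", and so "a letter from the primary care physician will ask the patient to read the letter and then give it to their caregiver". The same letter says that a research assistant will telephone "unless they do not want to be called".

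**Section 3.2.** A caregiver is an eligibility condition: "Patient must have someone who is identified as a family or friend who provides caregiving assistance".

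**Sections 1.2 and 5.2.1.** Randomisation is by cluster. A dyad enters the study only when patient and caregiver give verbal consent (or the patient assents).

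**Section 7.** Randomisation is expected to make covariate adjustment unnecessary, but the arms will be compared on demographic and clinical factors, including baseline Treatment Burden Questionnaire (TBQ) score, and unbalanced factors will be considered for adjustment.

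**The concern.** The two sections give staff different instructions about control patients. Under Section 5.1 they are written to before they are called; under the step list they are not.

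In a trial that randomises clinics and then asks each dyad for consent, recruitment is where selection can enter. Randomising clinics makes the eligible populations comparable in expectation. It does not make the consenting dyads comparable if the approach depends on arm. The step list already sorts patients by arm when the letter goes out, so allocation comes before the approach.

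What is at stake is who agrees to take part, and how caregivers answer the baseline survey if one arm has read about an improvement program and the other has not. TBQ, diabetes caregiver distress and the Dementia Severity Rating Scale all come from the caregiver and are collected at baseline (Table 1). Section 4 also plans to refresh the sample over the three years, so the ambiguity returns with each new dyad.

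**Working it through.** The plan gives no figure to reproduce. The check is a comparison of the two sections.

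| Item | Section 5.1 | Step list, Section 5.2.1 |
|---|---|---|
| Arms that get the letter | INT and CON | INT |
| Sender | RM | RA |
| Signed by | Primary care physician | Clinic director, lead physician or primary provider |
| Content | Program, possible survey, coming call | Program and its evaluation |
| Route to an unlisted caregiver | The letter, passed on by the patient | Telephone request to the patient, both arms |

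1. **Can both be true?** Not for control patients. The step list labels every step by arm, so the INT label on step 1 is a specific instruction and control recruitment starts at step 2. Section 5.1 names both arms. No other section resolves this.

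2. **Could these be two different letters?** Possibly, since sender and signatory differ. The reading is weak: both accounts describe a mailing that tells patients of the program and of its survey or evaluation. It would also leave the step list without the control mailing that Section 5.1 requires.

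3. **What follows if the step list governs?** Intervention patients receive a clinic-signed letter before the call. Control patients receive the call with no letter to hand to a caregiver and no written notice beforehand. Step 2 gives both arms the chart and the telephone as routes to the caregiver, so the gap is narrower than Section 5.1 alone suggests, but it remains.

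4. **What follows if Section 5.1 governs?** Both arms get the letter and this difference disappears.

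5. **Can the analysis repair it?** Partly. Section 7 can adjust for measured imbalance. It cannot adjust for unmeasured differences in willingness to take part. Baseline TBQ, one of its named balance factors, is itself caregiver-reported and could shift with what the caregiver has read.

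6. **Can it be sized?** If a letter brings in extra intervention dyads, the shift in an arm's mean or proportion is f × d. Here f is the share of that arm's dyads enrolled only because of the letter, and d is their outcome difference from the rest. The documents give neither, nor any uptake rate with or without a letter, nor the share of charts without a caregiver. The sign is open too: a letter may encourage some dyads and prompt others to decline, and d may be positive or negative.

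**The case against.** The strongest reply is that the difference is only potential and the plan already limits it. That is largely right. Several stronger readings are tempting, and the documents do not support them:

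- **That dyads do enter the arms by different routes.** This holds only if the step list is what staff follow. The text leaves the procedure undetermined.
- **That the letter decides who can meet the caregiver criterion.** Section 3.2 requires an identified caregiver, not one found by letter, and step 2 supplies other routes in both arms.
- **That control patients have no opt-out.** The opt-out in Section 5.1 is an institutional procedure run by a central office, and step 1 mentions none for intervention patients either. What control patients might lack is advance notice of it.
- **That intervention patients have their own clinician's endorsement.** That is one of three permitted signatories. The letter is not in the text reviewed, so its wording cannot be judged.
- **That the HbA1c outcome is biased because it is read only in consenting dyads.** Section 5.4 describes EHR entry for enrolled patients, but also a de-identified Epic extract on patients in both sets of clinics to evaluate effectiveness. The documents do not settle this.

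The contradiction stands, as does the selection risk if the step list is followed. Adjustment for measured factors reduces that risk without removing it.

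**Conclusion.** The contradiction is certain: Section 5.1 sends the letter in both arms and step 1 of Section 5.2.1 sends it in one. The consequence is conditional on step 1 being followed. In that case, recruitment differs by arm after allocation, and differences in who enrols and in caregiver-reported baseline measures can arise that cluster randomisation does not prevent.

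No number can be put on this from the documents, in size or direction, and any estimate of inflation in the primary outcome would rest on invented inputs. The point should be corrected because the risk is avoidable and the remedy is already implied by the protocol's own Section 5.1. It does not show that the trial's comparison is biased.

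**What to change.** 1. Mark step 1 of the step list INT and CON, to agree with Section 5.1, and name one sender and one rule for the signatory in both places.
2. Use the same arm-neutral letter in both arms, with the same content on the survey, the request to pass it to the caregiver and the opt-out, posted at the same interval before the research call.
3. Report by arm the numbers eligible, sent a letter, opted out, with no caregiver found, refused and enrolled. If enrolment has begun, the same counts for dyads already approached will help show whether recruitment differed.

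There is no need to hold back intervention program information until after the baseline survey. Section 4 has the panel manager contact dyads around clinic visits or as soon as they are identified, and provides for brochures; such a rule would cut across both.

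The cost is a wording change with IRB approval, the log needed for the counts, and postage to control patients, which Section 5.1 already implies.
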